11.3. Appendix 3: Derived and Transformed Data

11.3.1. General

Multiple Measurements at One Time Point

- Mean of the measurements will be calculated and used in any derivation of summary statistics but if listed, all data will be presented.

Study Day

- Calculated as the number of days from Visit 1 date:
 - Ref Date = Missing → Study Day = Missing
 - Ref Date < Visit 1 Date → Study Day = Ref Date – Visit 1 Date
 - Ref Date ≥ Visit 1 Date → Study Day = Ref Date – (Visit 1 Date) + 1

11.3.2. Study Population

Demographics

Age

- GSK standard IDSL algorithms will be used for calculating age where birth date will be imputed as follows:
 - Any subject with a missing date and month will have this imputed as '30th June'.
- Birth date will be presented in listings as 'YYYY'.
- The reference day for age calculation will be screening visit.

Body Mass Index (BMI)

- Calculated as $\text{Weight (kg)} / [\text{Height (m)}]^2$

11.3.3. Imaging

Imaging Parameters

All imaging parameters datasets will contain ROI which will include the side of the ROI where applicable. A variable will be derived for the side with the higher (named 'High') and lower (named 'Low') parameter value. When ROI does not have a side or in the case where the sides have equal parameter values the variable will be 'NA'. The variable can be called 'Side', to aid with the reporting of the study. For MRI parameters, the aggregated score will be included for listing and summary tables and plots. No derivations will be conducted by GSK.

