7.2. Pharmacokinetic Analyses

7.2.1. Overview of Planned Radio-Pharmacokinetic Analyses

The radio-PK analyses will be based on the PK population, unless otherwise specified. Influx rate constant (K_i) will be used as the imaging metric for ^{11}C -MET dynamic scan.

[Table 4](#) provides an overview of the planned Radio-PK analyses, with further details of data displays being presented in [Appendix 11](#): List of Data Displays.

Table 4 Overview of Planned Radio-Pharmacokinetic Analyses.

Endpoint / Parameter/ Display Type	Untransformed ¹				
	Stats Analysis		Summary	Individual	
	T	F	T	F	L
Radioactivity concentrations (whole blood and plasma)					
static ¹⁸ F-FDG PET/CT					Yes
¹¹ C-MET PET/CT			Yes	Yes ^{2,3}	Yes
Radiopharmacokinetic parameters (¹¹C-MET)					
Influx rate constant (K _i)	Yes ³	Yes ³	Yes		Yes
Administration Volume					
Tracer and contrast					Yes
Meal Ingested					
Totality of Meal ingested					Yes

NOTES:

- T = Table, F = Figure, L = Listings
- Stats Analysis = Represents TFL related to any formal statistical analyses (i.e. modelling) conducted.
- Summary = Represents TFL related to any summaries (i.e. descriptive statistics) of the observed raw data.
- Individual = Represents FL related to any displays of individual subject observed raw data.
- [1]: Log_e transform if necessary
- [2]: By subject group for ¹¹C-MET
- [3]: Correlation between radioPK parameter (K_i) vs ¹¹C-MET PET/CT SUV_{peak/mean/max} by the side of the gland with most/least uptake in and ROI.

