The histological scores (see Section 11.3.5) and the various disease indices (see Section 11.3.4) – ESSDAI, ESSPRI, Patient and Physician global assessment of disease activity, oral and ocular dryness scales will be descriptively summarized and listed for pSS group only.

Descriptive statistics will be calculated for the exploratory multiparametric MRI quantitative derived parameters listed in Table 7 (as data permits) and presented in tables. All parameters will be listed by group (and ROI, as data permits). Mean (\pm SE bars) will be plotted for each parameter by ROI (if appropriate with panel for each side).

Correlation between ^{18}F -FDG PET/CT (pSS subjects only), ^{11}C -MET PET/CT and MRI parameters (HV and pSS subjects) in the region of the salivary glands (parotid gland) will be explored using scatter plots. Plots will be in panel for each side (most vs least uptake) of the region scanned. The parameters will include, SUV_{peak} for PET/CT and K_{trans} , D and f for multiparametric MRI.

Furthermore, correlation between the imaging parameters mentioned above and

- histological scores (mean and maximum lymphoid organisation score and volume fraction) from the minor salivary gland biopsy
- Salivary flow rate – mean (from baseline and visit 2) stimulated and basal salivary flow rate, and mean difference (stimulated – basal)
- Measures of Disease Activity – ESSDAI and ESSPRI scores
- Lab biomarkers of disease activity – C3 and C4 levels
- Schirmer's test – length of paper wetted by eyes (panel for each side; least and most) and time to completely wet the strip (panel for each side; least and most).

may be explored using scatter plots (panel for each side) and statistical analysis summarised in tables. In addition, SUV_{peak} from the ^{11}C -MET PET/CT will be correlated with the ratio of IgG/IgA using scatter plots and summary tables of the correlation. See below for summary of correlations:

CONFIDENTIAL

203818

Method		11C-MET PET/CT	18F-FDG PET/CT	Multiparametric MRI
	Parameter(s)/Endpoint	SUVpeak	SUVpeak	(median) Ktrans, (median) D, (median) ADC, (median) f, (median) IRE, (median) ME, (mean) Lipid Content, (median) D* (pseudo diffusion), (mean) gland volume
11C-MET PET/CT	SUVpeak		Yes	
18F-FDG PET/CT	SUVpeak	Yes		
Multiparametric MRI	(mean) lipid content	Yes	Yes	Yes ¹
Histological scores	Max lymphocyte focus score	Yes	Yes	Yes
	Mean lymphocyte focus score			
	Max Lymphoid organisation grading			
	Mean Lymphoid organisation grading			

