11.11.7. Pharmacokinetic Tables

Pharmacokinetic: Tables					
No.	Population	IDSL / TST ID / Example Shell	Title	Programming Notes	Deliverable [Priority]
Radioactivity concentrations (static ¹⁸F-FDG and ¹¹C-MET)					
3.1.	PK	PKCT1	Summary of ¹¹ C-MET Tracer Pharmacokinetic Concentration Data	Paginated by Group and type of blood (Whole and Plasma). Group to include pSS, HV and overall. Subheading: 'Subject group: [group]' 'Blood: [blood type]'	SAC
Radiopharmacokinetic parameters					
3.2.	PK	PKPT1	Summary of Radiopharmacokinetic Parameter – Influx Rate Constant (K _i) from ¹¹ C-MET PET/CT	Paginated by Group Group to include pSS, HV and overall. Subheading: 'Subject group: [Group]'	SAC
3.3.	PK	EFF_T3	Summary of correlation between PK modelling index with ¹¹ C-MET PET/CT static imaging parameters	Paginated by Group Group to include pSS, HV and overall. Subheading: 'Subject group: [Group]' Change last three column titles to 'SUVpeak' 'SUVmean' and 'SUVmax' respectively. Footnote: Parotid gland side with the highest and lowest uptake values.	SAC

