11.11.8. Pharmacokinetic Figures

Pharmacokinetic : Figures					
No.	Population	IDSL / TST ID / Example Shell	Title	Programming Notes	Deliverable [Priority]
Radioactivity concentrations (static ¹⁸ F-FDG and ¹¹ C-MET)					
3.1.	PK	PKCF1P	Plot of Individual ¹¹ C-MET Tracer Pharmacokinetic Concentration-Time (Linear and Semi-Log)	Paginated by Group and type of blood (Whole and Plasma). Group to include pSS, and HV. Subheading: 'Subject group: [group]' Blood: [blood type]	SAC
Radiopharmacokinetic parameters					
3.2.	PK	EFF_F4	Plot of Individual Radiopharmacokinetic Parameter Influx Rate Constant (K _i) versus Standardised Uptake Value of ¹¹ C-MET PET/CT	Paginate by parameters SUVpeak, SUVmean and SUVmax ROI: Parotid Gland Plot Ki along X axis and SUV parameter value along Y axis. Colour by subject group. Panel by sides – side with higher parameter values and side with lower parameter values. Include Pearson's product moment correlation	SAC

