5.11.	Safety	EFF_T3	Summary of Correlation Between Length Wet per Minute (mm/min) from Schirmer's Test and Imaging Parameters.	
Add column for subjects group.
 
Pearson's and Spearman's correlation summary by subject group to be provided in the summary table.
 
Imaging parameter from the parotid gland, and include variable for side (Left or Right).
 
PET/CT parameter: SUVpeak
 
Subheading 'Schirmer's test: [name]'
 
Footnote: 'Note: Ratio calculated as length (mm) paper wet divided by time taken to wet (min). The Ratio is presented as strip length wet per minute.'
 
Note: The side of the eye for the Schiremr's test is correlated with the same side of the imaging parameter.'
	SAC

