5.9.	Safety	EFF_F5	Plot of Imaging Parameters vs Imaging Parameters Obtained from Different Imaging Technique.	Symbol by subject group where applicable. Panel by side of the gland : low/high/aggregated Paginate by plots type with subheading of parameters being compared: FDG (SUVmean) vs CMET(SUVmean), FDG(SUVmax) vs CMET(SUVmax), FDG(SUVpeak) vs CMET(SUVpeak), CMET(SUVpeak) vs MRI(Mean Lipid content) FDG(SUVpeak) vs MRI(Mean Lipid Content) MRI(Mean Lipid Content) vs MRI(Median; Ktrans, IRE, ME, D, f, D* and ADC)	SAC

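### SAP 11.3.3 ranks High and Low side by each parameter's own value, so followed literally the High and Low panels of Figure 5.9 can plot opposite glands on the two axes (minor)

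*SAP*

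**What the plan says.** SAP 11.3.3 covers all imaging parameter datasets: "A variable will be derived for the side with the higher (named 'High') and lower (named 'Low') parameter value". Its tie rule, "in the case where the sides have equal parameter values the variable will be 'NA", likewise compares a parameter only with itself. The paragraph ends by stating that GSK performs no derivations.

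Figure 5.9 (SAP 11.11.11) plots imaging parameters against each other with the instruction "Panel by side of the gland : low/high/aggregated". It lists 12 pairs:
- three FDG against MET (SUVmean, SUVmax, SUVpeak);
- two PET SUVpeak against lipid content;
- seven lipid content against another MRI parameter.

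SAP 9.1.1 says of these plots: "Plots will be in panel for each side (most vs least uptake) of the region scanned". Similar wording governs the Ki against SUV displays: "by the side of the gland with most/least uptake in and ROI" (Table 4, note 3), "Parotid gland side with the highest and lowest uptake values" (Table 3.3) and "side with higher parameter values and side with lower parameter values" (Figure 3.2).

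For Schirmer's test the rule is explicit. Table 5.11 and Figure 5.8 work by left and right, and the eye "is correlated with the same side of the imaging parameter".

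**The concern.** A side label ranked within one parameter is harmless while that parameter is shown alone, or against a measure with one value per subject. It becomes ambiguous when two ranked parameters share a scatter plot, because each may rank the glands differently.

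Protocol 4.4 asks whether inflammatory change affects protein synthesis within the glands, and whether synthesis is reduced in a gland without inflammation. Those are same-gland questions. If the High panel mixes left and right, its r describes something else. It may be weaker than the same-gland r, stronger, or occasionally of opposite sign. Figures 2.4 and 2.9 and section 7.1.1.3 show left-right asymmetry one parameter at a time, so they do not supply the missing view.

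**Working it through.** **1. Literal reading, worked on one invented subject.** FDG SUVpeak is left 3, right 2, so High is left. MET SUVpeak is left 4, right 6, so High is right. The High panel plots (3, 6), left gland against right. The Low panel plots (2, 4), right against left. Same-gland pairing would give (3, 4) and (2, 6).

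**2. Does other text settle it?** The most-versus-least wording in 9.1.1 could mean one chosen gland. It does not say whose ranking applies when two parameters are plotted, and lipid content, D and ADC are not tracer uptake. Explicit same-side pairing is written only for Schirmer's test.

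**3. Model for size.** The plan states no figure to reproduce, and the documents give no left-right or between-parameter correlations. All inputs below are therefore assumed.

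Each value is √ICC·B + √(1−ICC)·W, normal, with W independent between left and right. Let b be the between-subject correlation of the two parameters and w their gland-level correlation. With S = left + right and D = left − right, the maximum is (S + |D|)/2. Then:
- Same-gland r = ICC·b + (1−ICC)·w
- High-High r = [4·ICC·b + 2(1−ICC)w + 2(1−ICC)(2/π)(√(1−w²) + w·asin w − 1)] / [2(1+ICC) + 2(1−ICC)(1−2/π)]; Low-Low is equal by symmetry
- Share of subjects with opposite glands paired = arccos(w)/π

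**4. One case in full: ICC 0.5, b = 0, w = -0.8.**
- Same gland: 0.5 × (-0.8) = -0.40.
- High-High numerator: -0.8 + 0.637 × (0.6 + 0.742 − 1) = -0.582.
- High-High denominator: 3 + 0.363 = 3.363. So r = -0.17.
- Opposite-gland share: arccos(-0.8)/π = 80%.
- A 20,000-replicate simulation at n = 12 gave mean r of -0.39 (same gland) and -0.17 (both High-High and Low-Low).
- The Fisher 95% interval around r = -0.40 at n = 12 is tanh(-0.424 ± 1.96/3) = -0.79 to +0.23, which contains -0.17.

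**5. Other cases.**

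| ICC | b | w | Same gland | High-High |
|---|---|---|---|---|
| 0.9 | -0.5 | -0.5 | -0.50 | -0.49 |
| 0.5 | +0.5 | +0.5 | 0.50 | 0.47 |
| 0.7 | +0.5 | -0.8 | 0.11 | 0.29 |
| 0.3 | +0.5 | -0.8 | -0.41 | -0.07 |

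The opposite-gland share is 67%, 50%, 33% and 20% at w = -0.5, 0, +0.5 and +0.8.

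**6. Whole grid** (ICC 0.3, 0.5, 0.7, 0.9; b -0.5, 0, +0.5; w -0.8, -0.5, 0, +0.5, +0.8; 60 cells). The correlation is attenuated in 36, inflated in 18, reversed in 2 (-0.20 to +0.004 and -0.15 to +0.12) and unchanged in 4. The median absolute shift is 0.06. It exceeds 0.1 in 21 cells: 9, 7, 5 and 0 of 15 as ICC rises from 0.3 to 0.9. Of those 21, 15 have negative w.

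**7. Ki against SUV.** With b = w = 0.9 and ICC 0.7, r moves from 0.90 to 0.89.

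**The case against.** **The rule may exist elsewhere.** Because 11.3.3 disclaims derivation by GSK, the labels may arrive from the imaging vendor, as Ki does under 7.2.2.1. Section 11.3.3 also describes a single variable, and 9.1.1 can be read as naming one gland. This stands: a reader might infer that the axes will be crossed, but the documents show only that the stated rule permits it.

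**Maximum against maximum is meaningful.** This also stands. A reader might conclude that the High and Low panels could not be interpreted. They could, as subject-level summaries, but they would answer a different question from the one in protocol 4.4.

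**The size depends on invented inputs.** True. With w at or above zero, only 6 of 36 cells shift by more than 0.1, and 5 of those combine it with b = -0.5. In 11 of the 21 larger shifts b and w have opposite signs. The documents support no particular combination; protocol 2.2 calls the relation between inflammation and gland function unclear.

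**Little depends on it.** Figure 5.9 is exploratory, no correlation table in the SAP reports imaging against imaging, and no hypotheses are tested. Left and right values are listed for every subject (shell EFF_L1), so same-gland pairs can be rebuilt by hand. This supports a minor grading. It does not supply the missing rule.

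**Conclusion.** The point holds as a minor gap in specification. The written rule allows opposite glands on the two axes in two of the three panels of Figure 5.9, and no cited document closes that gap. That conclusion rests on the text alone. The effect on r rests wholly on assumptions: usually small, material mainly when gland-level correlation is negative and the left-right correlation is moderate or low, and hard to distinguish from sampling error with 8 to 12 pSS subjects.

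A reader might extend this to a general bias in the SAP's correlations. The documents do not support that. The aggregated panel uses one combined value per subject. Salivary flow, ESSDAI, ESSPRI, histology and C3/C4 have no gland side to mismatch. Ki against SUV shares the loose wording but is negligibly affected under the strong correlation assumed above.

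**What to change.** In Figure 5.9 and section 9.1.1, require the same anatomical gland on both axes, by one of two routes:
- Pair left with left and right with right, as for Schirmer's test. This is the simpler route.
- Fix one index side per subject from a named parameter measured in every plotted subject, and use that side on both axes. This keeps the most/least contrast but still attenuates r somewhat: in the case worked in full, -0.31 against -0.40 for same-gland pairing and -0.17 for High-High.

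If a vendor document already fixes the side, cite it in 11.3.3. Keep the aggregated panel. Table 3.3 and Figure 3.2 need no change on grounds of size.

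The cost is one sentence and at most one derived variable, to be agreed with whoever supplies the side labels. No new data are needed.

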Published literature around use of  $^{18}\text{F}$ -FDG,  $^{11}\text{C}$ -MET PET and multi-parametric MRI in pSS is limited as the methods are more commonly used in other indications:  $^{18}\text{F}$ -FDG uptake is a marker for increased glucose uptake, which is closely correlated to certain types of metabolism such as that of malignant cells but it is also a feature of inflammation with inflammatory foci exhibiting high  $^{18}\text{F}$ -FDG uptake [Bakheet, 1998]. In pSS, the relation of  $^{18}\text{F}$ -FDG uptake to inflammation needs to be further explored but a recent report by Ziakas [Ziakas, 2014] showing a strong correlation between inflammation and FDG uptake in Sjögren's patients treated for salivary lymphomas is encouraging [Ziakas, 2014]. In addition, Cohen *et al.* [Cohen, 2013] reviewed the PET data from 32 Sjögren's patients that underwent  $^{18}\text{F}$ -FDG PET and showed that  $^{18}\text{F}$ -FDG uptake was increased in 75% of patients with 60% displaying increased uptake in lymph nodes, 50% in the parotid glands, 28% in the submandibular glands, 28% in the lung and 6% in the thyroid.

Salivary gland disease is a hallmark for pSS and PET with  $^{11}\text{C}$ -MET can potentially assess function with a superior sensitivity and anatomical resolution than the gold standard contrast sialography or salivary gland scintigraphy with  $^{99\text{m}}\text{Tc}$ -sodium pertechnetate.  $^{11}\text{C}$ -MET, a labelled essential amino acid, is most popular for PET imaging of brain tumours; events such as cellular proliferation are associated with increased protein synthesis and hence avid uptake of these precursors [Glaudemans, 2013]. Furthermore,  $^{11}\text{C}$ -MET has been used for measuring liver protein synthesis and assessing excretory pancreas function [Harris, 2013]. Dynamic  $^{11}\text{C}$ -MET has been used as a quantitative measure of regional gland function in the major salivary glands in head-and-neck cancer patients that underwent loss of salivary gland function as a result of radiotherapy [Buus, 2004]. This study aims to determine whether there is a disturbance in protein synthesis in salivary glands that correlates to disease activity, although the relationship between inflammation and gland function (protein synthesis) in

pSS is as yet unclear. In addition, the ability of PET to image the whole body will also allow recording of function in other glands such as the pancreas.

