7. PRIMARY STATISTICAL ANALYSES

7.1. Imaging Analyses

7.1.1. Overview of Planned Imaging Analyses

The imaging analyses will be based on the Safety population, unless otherwise specified.

Table 3 provides an overview of the planned imaging analyses, with full details of data displays being presented in Appendix 11: List of Data Displays.

Table 3 Overview of Planned Imaging Analyses

Endpoint / Parameter	Untransformed						
	Stats Analysis			Summary		Individual	
	T	F	L	T	F	F	L
¹⁸F-FDG PET/CT semi-quantitative parameters							
SUV _(mean/max/peak) , T/R Ratio, TIV				Yes ¹	Yes ¹	Yes ¹	Yes ¹
¹¹C-MET PET/CT semi-quantitative parameters							
SUV _(mean/max/peak) , T/R Ratio, TIV	Yes ³	Yes ³		Yes ²		Yes ²	Yes ²
Multiparametric MRI quantitative parameters							
K _{trans} ⁴ , ADC ⁴ , D ⁴ and f ⁴	Yes ³	Yes ³		Yes ²		Yes ²	Yes ²

NOTES:

- T = Table, F = Figure, L = Listing
- SUV = Standard Uptake Value, T/R Ratio = Tissue-to-reference ratio, TIV = Total Inflammatory Volume (TIV), K_{trans} = Exchange rate, ADC = Apparent Diffusion Coefficient, f = Microvascular volume fraction D = Pure Diffusion Coefficient
- Stats Analysis = Represents TFL related to any formal statistical analyses (i.e. modelling) conducted.
- Summary = Represents TFL related to any summaries (descriptive statistics) of the observed raw data.
- Individual = Represents FL related to any displays of individual subject observed raw data.
- 1: By region of interest (ROI)
- 2: By region of interest (ROI) and group (Healthy Volunteers (HV) or primary Sjogren's Syndrome (pSS) patient).
- 3: If data permits. Stats analysis for SUV_{mean/max/peak} for ¹¹C-MET PET/CT and K_{trans}, D and f for MRI.
- 4: Median and IQR (Interquartile Range) values for each parameter will be used.

7.1.1.1. ¹⁸F-FDG PET/CT

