Descriptive statistics will be calculated and presented graphically and in tabular format for ¹⁸F-FDG semi-quantitative derived parameters including SUV, Tissue-to-reference ratio and TIV (as data permits). All parameters will be listed by ROI (where ROI will be sorted by relevance to pSS subjects and ordered as Parotid gland, lacrimal, submandibular and lastly any other gland in alphabetical order). When applicable for a given ROI, the outputs will be separated by the side of the ROI having higher parameter values and lower parameter values. Aggregated measures (left-right combined) will use measures extracted over the combined ROI's, rather than left-right averages to not introduce a bias towards the smaller gland.

The data may be further explored using scatter plots to examine asymmetry in parameter values between left and right parotid glands.

Further details are given in [Appendix 11](#): List of Data Displays.

7.1.1.2. ¹¹C-MET PET/CT

Statistical analysis comparing the subject group (HV or pSS patient) will be conducted for ¹¹C-MET PET/CT parameters (including but not limited to SUV_{mean} , SUV_{max} and SUV_{peak} , as data permit), see Section 7.1.2 for detail.

Descriptive statistics will be calculated and presented graphically and in tabular format for ¹¹C-MET semi-quantitative derived parameters including SUV, Tissue-to-reference ratio and TIV and size of abnormality (as data permits). All parameters will be listed by group (HV or pSS patient) and ROI (where ROI will be sorted by relevance to pSS subjects and ordered as Parotid gland, lacrimal, submandibular and lastly any other gland in alphabetical order). When applicable for a given ROI, the analysis and summary outputs will be separated by the side of the ROI having higher parameter values and lower parameter values. Aggregated measures (left-right combined) will use measures extracted over the combined ROI's, rather than left-right averages to not introduce a bias towards the smaller gland.

The data may be further explored using scatter plots to examine asymmetry in parameter values between left and right parotid glands.

Further details are given in [Appendix 11](#): List of Data Displays.

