7.1.2. Planned Imaging Statistical Analyses

Primary Statistical Analyses
Endpoint(s)

 • ¹¹C-MET PET/CT derived parameters, including but not limited to SUV_{peak}, SUV_{mean}, SUV_{max} • Multiparametric MRI derived parameters, including but not limited to (median and IQR) K_{trans}, (median and IQR) Pure diffusion coefficient (D), (median and IQR) microvascular volume fraction (f) and (median and IQR) ADC.
Model Specification

 • Parameters will be statistically analysed individually using an Analysis of Variance (ANOVA) model. • Terms fitted in the ANOVA model will include: Fixed categorical : Subject group (HV or pSS patient)
Model Checking & Diagnostics

 • Refer to Appendix 9: Model Checking and Diagnostics for Statistical Analyses : Model Checking and Diagnostics for Statistical Analyses.
Model Results Presentation

 • Estimates of Difference (pSS-HV) (or Ratio (pSS/HV) if log_e transformed) and 95% confidence interval for the derived parameters will be presented by ROI¹. • Plots of means (difference or ratio) and 95% confidence interval from the model will be generated for each ROI. • P-values will not be presented as formal hypothesis is not being tested. The interpretation will be based on point estimates and its precision (95% CI).

NOTES :

- [1]: When applicable for a given ROI, the analysis will be separated by the side of the ROI having higher parameter values and lower parameter values, and aggregated over both sides.

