11.12. Appendix 12: Example Mock Shells for Data Displays

Example : EFF_T1
 Protocol : 203818
 Population : Safety

Page 1 of n

Table 2.1
 Summary of ¹⁸F-FDG PET/CT parameters

Parameter: Parameter 1

Region of Interest	Sides	Group	N	n	Mean	SD	SE	Q1	Median	Q3	Min.	Max.
ROI 1	Low	pSS	xx	xx	xx.x	xx.xx	xx.xx	xx.x	xx.x	xx.x	xx	xx
		HV	xx	xx	xx.x	xx.xx	xx.xx	xx.x	xx.x	xx.x	xx	xx
	High	pSS	xx	xx	xx.x	xx.xx	xx.xx	xx.x	xx.x	xx.x	xx	xx
		HV	xx	xx	xx.x	xx.xx	xx.xx	xx.x	xx.x	xx.x	xx	xx
ROI 2	NA	pSS	Xx	Xx	xx.x	xx.xx	xx.xx	xx.x	xx.x	xx.x	xx	Xx
			xx	xx	xx.x	xx.x						

Note: NA: Sides are not applicable for all ROI.

Programming Note: Include Groups as a separate column next to Sides for 11C-MET PET/CT parameters summary.

Example : EFF_T2
Protocol : 203818
Population : Safety

Page 1 of n

Table X.X

Summary of Disease Activity (pSS only)

Disease Activity	N	n	Mean	SD	Median	Minimum	Maximum
------------------	---	---	------	----	--------	---------	---------

ESSDAI score

ESSRPI score

Patient Global assessment (VAS)

Physician Global Assessment (VAS)

Oral dryness numerical rating

Ocular dryness numerical rating

Example : EFF_T3
 Protocol : 203818
 Population : Safety

Page 1 of n

Table x.x

Summary of Correlation Between Disease Activity and Imaging Parameters

Disease Activity: [name of index]

Scan / Parameter	Side	Pearson's correlation / 95% CI	Spearman's correlation / 95% CI
¹¹ C-MET / SUVpeak	High	x.xx / (x.xx, x.xx)	x.xx / (x.xx, x.xx)
	Low	x.xx / (x.xx, x.xx)	x.xx / (x.xx, x.xx)
F-FDG / SUVpeak	High	x.xx / (x.xx, x.xx)	x.xx / (x.xx, x.xx)
	Low	x.xx / (x.xx, x.xx)	x.xx / (x.xx, x.xx)
MRI / Ktrans	High	x.xx / (x.xx, x.xx)	x.xx / (x.xx, x.xx)
	Low	x.xx / (x.xx, x.xx)	x.xx / (x.xx, x.xx)

Example: EFF_T4
Protocol: 203818
Population: Safety

Table x.xx

Point estimate and 95% CI for [imaging method] Derived Parameter of Difference in pSS vs. HV
95% CI for

ROI: [] Side: []

N	Group	n	Mean	Standard Error	Difference from HV	Difference (Lower, Upper)
xx	HV	xx	x.xx	x.xxx		
xx	pSS	xx	x.xx	x.xxx	x.xx	(x.xx, x.xx)
xx	HV	xx	x.xx	x.xxx		
xx	pSS	xx	x.xx	x.xxx	x.xx	(x.xx, x.xx)

Example: EFF_T5
 Protocol: 203818
 Population: Safety

Summary of the Posterior Distribution of the Ratio and Difference of Group Means for [Imaging method] parameters by Region

Parameter	ROI	Group	Prior Distribution for Θ	Value of σ used in the model	Posterior distribution					
					Mean	SD	Median	25th quartile	75th quartile	95% Credible Interval

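### SAP 11.3.3 codes subjects with equal left and right values as NA, so they drop out of the High and Low strata; the main exposure is the descriptive TIV summaries

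*SAP*

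**What the plan says.** SAP 11.3.3 (Imaging) derives a Side variable from the parameter value: High for the side with the larger value and Low for the other. It then sends two different situations to one code: a region with no side, and, "in the case where the sides have equal parameter values the variable will be" NA, a paired region whose two sides tie.

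That variable is used widely:

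- For 18F-FDG in SAP 7.1.1.1, "the outputs will be separated by the side of the ROI having higher parameter values and lower parameter values". SAP 7.1.1.2 (11C-MET) and 7.1.1.3 (MRI) contain the same instruction and extend it to the analyses.
- For the pSS versus healthy volunteer ANOVA in SAP 7.1.2, "the analysis will be separated by the side of the ROI having higher parameter values and lower parameter values, and aggregated over both sides".
- Most correlation displays in SAP Appendix 11 are also split by High and Low, usually with an aggregated level.

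Mock shell EFF_T1, used for the PET summaries (Tables 2.1 and 2.2), gives a paired region Low and High rows only. Its footnote reads "NA: Sides are not applicable for all ROI", which describes regions without sides and says nothing of ties. SAP 11.4.2 covers missing data but not ties. Nowhere does the SAP place a tied value in both strata.

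**The concern.** When left equals right, the higher and the lower value are both known and are the same number, so there is no statistical reason to leave the subject out of either stratum. Under the rule as written the subject is in neither.

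The subjects affected are not a random subset. For a continuous parameter they are the most symmetric ones. For TIV, a primary endpoint for both tracers, an exact tie arises naturally if both glands have no volume above threshold and that is stored as 0. The High and Low TIV summaries would then describe only patients with some inflamed volume, while appearing to describe all pSS patients scanned. For FDG this matters more than usual, because only pSS subjects are scanned and the descriptive summaries are the primary analysis.

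**Working it through.** **Baseline precision.** The documents give no figure for ties. The nearest is Protocol Table 5, the half-width of a 95% confidence interval for a mean: t(0.975, n−1) × SD / √n. With SD = 1:

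- n = 4: 3.182 / 2 = 1.59
- n = 8: 2.365 / 2.828 = 0.84
- n = 12: 2.201 / 3.464 = 0.64 (0.635 unrounded)

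These match the table. If k of 12 subjects tie and leave a stratum, the half-width at SD = 1 becomes 0.72 (k = 2), 0.84 (k = 4), 1.05 (k = 6) or 1.59 (k = 8). In a healthy volunteer group of 4, one tie moves it from 1.59 to 2.48. If the tied value is carried into both strata, nothing changes from the baseline.

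**TIV.** Two assumptions, neither stated in the documents: absent volume is stored as 0, and absence of raised uptake means TIV = 0. Let p be the share of patients with TIV above 0 on at least one side, and m the mean High value among them.

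- Mean over all patients: p × m + (1 − p) × 0 = p × m
- Mean over patients left after ties are removed: m
- Ratio: 1/p. The same ratio holds for Low, since every value removed is 0.

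As a proxy for p, Protocol 2.2 cites a cohort of 32 patients with raised FDG uptake in "50% in the parotid glands, 28% in the submandibular glands".

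| Gland | p | Inflation 1/p | Expected ties, n = 8 | Expected ties, n = 12 |
|---|---|---|---|---|
| Parotid | 0.50 | 2.0 | 4.0 | 6.0 |
| Submandibular | 0.28 | 3.6 | 5.8 | 8.6 |

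For the parotid, the chance of at least one tie among 8 patients is 1 − 0.5^8 = 0.996. For the submandibular gland, the chance that 2 or fewer of 12 patients remain is 0.30.

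A made-up set of 12 shows the mechanism: six patients at 0/0, and six at 2/1, 4/0, 6/5, 3/4, 5/0 and 8/6. The High values of the last six sum to 29. Mean High is 29/12 = 2.42 over all patients and 29/6 = 4.83 under the rule; the median moves from 1.0 to 4.5. Mean Low moves from 15/12 = 1.25 to 15/6 = 2.5.

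**SUV and MRI parameters.** Here ties come from rounding. Correlated normal left-right pairs were simulated with an assumed correlation of 0.80 to 0.95, using means and SDs from the literature table in Protocol 9.2 (11C-MET SUVmax 6.00, SD 1.5; Ktrans 0.26, SD 0.05).

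| Parameter | Decimals kept | Share of subjects tied |
|---|---|---|
| SUV | 1 | 4.2% to 8.3% |
| SUV | 2 | 0.4% to 0.8% |
| Ktrans | 2 | 12.6% to 24.5% |
| Ktrans | 3 | 1.3% to 2.5% |

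For 12 subjects, SUV at one decimal means 12 × 0.042 = 0.5 to 12 × 0.083 = 1.0 subject; at two decimals, at most 12 × 0.008 = 0.1. The documents do not give the precision at which the imaging values will be supplied.

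**The case against.** The best reply is that the rule's reach is limited, and much of that stands.

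A reader might infer that patients with zero TIV also leave the pSS versus healthy volunteer comparisons. The documents do not support this. Note 3 to SAP Table 3 lists "Stats analysis for SUV_{mean/max/peak} for ¹¹C-MET PET/CT and K_{trans}, D and f for MRI", and the programming note for Table 2.3 names SUVs only. FDG has no group comparison. The planned PET correlations use SUVs. Side follows the parameter value, so a patient tied on TIV would normally have unequal SUVs and stay in the SUV analyses. The open-ended endpoint wording in SAP 7.1.2 leaves a TIV comparison possible, but none is specified.

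A reader might also infer that tied subjects vanish from the report, or that asymmetry will be exaggerated throughout. That goes too far. They remain in the listings, in the aggregated models and MRI displays, and in most correlation displays, which have an aggregated level. Figures 2.4 and 2.9 plot each subject's left/right SUVpeak ratio without using Side, so a subject tied on SUVpeak sits on the reference line at 1. NA is a printed level in EFF_T1, and N and n are shown, so a shortfall could be noticed. The SAP does not say that NA records are deleted.

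The cover is incomplete, however. EFF_T1 has no aggregated row for the PET summaries, 11.3.3 assigns the aggregated value to MRI displays, and Tables 3.3 (Ki with SUV) and 5.9 (histology) specify high and low sides only. An NA row holding tied parotid subjects would carry a footnote that misdescribes them, and the High and Low rows would still lack them.

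Finally, the TIV sizes are conditional. TIV is reported only where anatomically relevant and as data permit, and absent volume might be stored as missing. The cited rates are for raised uptake in another cohort, whereas this trial requires ESSDAI of at least 5. This objection stands in full against treating 2.0 and 3.6 as forecasts.

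**Conclusion.** The point holds, and it is minor. SAP 11.3.3 states an explicit rule that leaves tied subjects out of the High and Low strata, for no statistical gain, and uses one code for two different situations.

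The consequence that could matter is upward bias in the descriptive High and Low TIV summaries and figures, by 1/(share of patients with TIV above 0). The size depends entirely on absent TIV being stored as 0; the 2.0-fold and 3.6-fold values also depend on cited uptake rates standing in for that share. If absent TIV is stored as missing, this mechanism does not operate, but the reader still needs to be told which patients the summary covers.

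For the 11C-MET SUV and MRI analyses the loss is confined to the High and Low strata, and is small unless values are rounded coarsely relative to their spread. In an exploratory pilot with no hypothesis tests, none of this threatens the study's conclusions.

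**What to change.** Amend SAP 11.3.3 in three respects:

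1. When left and right values are equal, including 0 and 0, carry the common value as both the High and the Low record.
2. Reserve NA for regions that have no sides, which also makes the EFF_T1 footnote correct as it stands.
3. State whether a gland with no volume above threshold has TIV recorded as 0 or as missing.

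The cost is a sentence or two in the SAP and one line of dataset code. No extra data are needed, and nothing changes for subjects whose sides differ. It should be done before database freeze, the SAP's own deadline for decisions on the final analysis.
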